## **8.2 Baseline Evaluations (Day 0)**

Following the screening visit, subjects determined to be eligible for participation in the study will undergo baseline assessments. Baseline evaluations will be performed upon admission to the clinical research unit on Day 0.

Baseline assessments include the following:

- Confirm eligibility
- Vital signs
- Weight measurement
- Concomitant medications
- Urine pregnancy test (if applicable)
- S-CAT
- C-CAT

Once subjects are confirmed to be eligible, they will be randomized to one of the treatment groups based on the randomization schedule.

## **8.3 Study Randomization**

Subjects will be randomized to each treatment group according to a predefined randomization scheme in a ratio of 1:1:1 among eight (8) to twelve (12) clinical sites. Assignment to treatment group will be disclosed only after subject eligibility is confirmed and immediately prior to injection treatment. The Investigator, clinical staff and the subjects will be blinded to treatment group.

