## **2.2 Description of Study Design**

This is a Phase 2b, double-blind, randomized, three-arm, placebo-controlled study that will consist of a screening period, baseline period, and a randomized treatment period.

Subjects will receive a single treatment session that consists of multiple injections of RZL-012 or placebo (Tween-80, propylene glycol, benzyl alcohol, and water) into the submental area under the chin, after which they will be monitored for safety and efficacy over 84 days.

Following the Day 84 visit of the last subject, subjects from three (3) chosen clinical sites will be followed up further twice up to a 1 year after injection to evaluate the long term safety and efficacy. The additional follow up visits will be at 6 and 12 months after injection.

For subjects from all sites that their adverse events were not resolved by Day 84, an unscheduled visit will be set 6-8 weeks after Day 84 to verify the resolution of the AE. On that visit, follow up of efficacy using C-CAT and S-CAT will also be conducted.

Each subject will be randomized to either active treatment (high or low dose RZL-012) or placebo at a ratio of 1:1:1 per group and receive one of the following:

- low dose (concentration of injected solution 34 mg/mL RZL-012) of 5.1 mg/0.15 mL/injection point that results in a dose/volume of  $163.2 \pm 20.4$  mg/4.8  $\pm 0.6$  mL RZL-012,
- high dose (concentration of injected solution 50 mg/mL RZL-012) of 7.5 mg/0.15 mL/injection point that results in a maximum total dose/volume of  $240 \pm 30$  mg/4.8  $\pm 0.6$  mL RZL-012,
- placebo of 0.15 mL/injection point that results in a total maximum volume of 4.8  $\pm 0.6$  mL.

Screening period: Subjects will undergo screening within 28 days prior to entering into the study.

Screening period will contain 2 visits, pre-screening visit to verify that subject qualifies the study based on S-CAT , C-CAT and 2D photography and another visit that will include an assessment of eligibility by measurement of SMF thickness using calipers, skin type by Fitzpatrick scale, subject's satisfaction scale related to appearance of SMF, subject impact questionnaire, and MRI. MRI will be conducted prior to the baseline visit. ECG and blood samples will also be conducted during the second screening visit.

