**Table 4: Dosing Regimen**

[figure not shown]
	N=135		
	RZL-012 High dose (50mg/mL)	RZL-012 Low dose (34mg/mL)	Placebo
Number of subjects (N)	45	45	45
Maximum RZL-012 dose (mg)/volume (mL)	270mg/5.4 mL	183.6 mg/5.4 mL	0mg/5.4±0.6mL
RZL-012 Dose (mg)/volume (mL) per single injection	7.5mg/0.15mL	5.1mg/0.15mL	0mg/0.15mL
Number of Injections per subject	32±4, maximum of 36		

Subjects treated with RZL-012 will undergo a single treatment session with  $32\pm4$  injections. The maximal number of injections will be 36 with maximal doses of 183.6 mg and 270 mg for the low and high doses, respectively. Each injection point will be dosed with 5.1 mg RZL-012 for the low dose or 7.5 mg for the high dose in a volume of 0.15 mL/injection site. Placebo subjects will be injected with a 0.15 mL placebo per each injection site. The maximal injection volume for all groups will be up to 5.4 mL.

Subjects will be injected with RZL-012 or placebo perpendicularly ( $90^\circ$ ) to the skin. An ice pack will be placed on the injected area for pain relief immediately after injection. Subjects will remain seated in the injection position for an additional 10 minutes after dosing.

The injection pattern will be based on a submental area shaped grid in which the distance between rows and columns will be 1 cm, as seen in Figure 7 below. The Investigator will choose  $32\pm4$  sequential points on the grid that will mark the injected area according to SMF fullness and convexity. The treatment area boundary: superiorly by a line 1 cm inferior to the mandibular margin, laterally by the sternocleidomastoid muscles, and inferiorly by the hyoid bone.

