#### 4.11 Clinician-Chin Assessment Tool (C-CAT)

SMF ratings using the C-CAT will be conducted by the Investigator at screening and baseline and at study visits on Days 28, 56, and 84 to assess the change in SMF severity before and following treatment.

The C-CAT score will be based on the Investigator's clinical evaluation of the subject in the Frankfurt horizontal plane. Clinical evaluation will include palpation of the chin and neck area, anterior, oblique and profile views of the chin and neck, and observation of pronation, supination, and lateral movement of the head. The score will be determined using the rating scale definitions. The score will be recorded as a whole number. At screening, the score will be used in conjunction with inclusion criteria.

The C-CAT is defined below. The scale is A 5-point scale (scored 0-4).

The grading system categorizes 3 aspects of submental chin fat: bulge, (size of the submental fat bulge) neck (extension of the bulge into the neck, downward and lateral) and jawline (the appearance of the jawline, presence of fat and definition of the jawline).

Each grade contains a description and a line drawing. Each grade is distinct and non-overlapping.

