## 8.5 Drug Administration

RZL-012 or placebo will be supplied as a single treatment in multiple sites of injection (32±4 injections). The injection dosing regimen and technique is crucial for the therapy safety.

The following procedures prior to injection into the SMF will be applied:

1. The lower face and anterior neck will be cleaned with an appropriate topical antiseptic.
2. Ice/cold pack or topical local anesthesia (i.e., lidocaine cream) may be used prior to drug administration to enhance subject's comfort.
3. The treatment area will be bounded superiorly by a line 1 cm inferior to the mandibular margin, laterally by the sternocleidomastoid muscles, and inferiorly by the hyoid bone.
4. Injection grid pattern will be applied by pressing the grid firmly onto the clean, dry skin, with the printed grid pattern facing the skin. The grid paper backing will be thoroughly wetted with a cotton pad soaked with sterile water. After 15 seconds, the grid cover will be peeled off.
5. An area of 32±4 adjacent injection points will be determined following the Investigator's evaluation.
6. Syringes will be filled with 1 mL RZL-012 high dose or low dose or placebo and the number of syringes will be compatible with the total volume of injection. Up to six (6) syringes for a total volume of 5.4 mL will be used.
7. All injections will be administered perpendicularly in 90 degrees, using a 1 mL Luer-lock syringe and a 29G x 1/2" needle, respectively.
8. The hole of the needle should be pointing into the fat layer and the injection direction should be towards the earth. An attempt to pull the plunger should be made prior to injecting to ensure no blood is coming out. If so, the plunger should be pushed down to inject 0.15 ml the medicine. The formulation is viscous; therefore, resistance is expected during injection.
9. Immediately following completion of the injections, an ice/cold pack will be applied for immediate pain relief. It will be held by the subject for at least two (2) minutes.
10. The Investigator will record the number of injections administered for each subject.

The injection pattern used will be based on an existing grid in the shape of the submental area, where distance between injection rows will be 1 cm and distance between the injection columns will be 1 cm.

The number of injections for each subject will be determined by the Investigator according to fullness of SMF but will not be lower than 28 injections or higher than 36 injections.

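### Protocol 8.3 says treatment assignment is disclosed just before injection, then blinds everyone at the site; it must state what is released and to whom, and the kit descriptions must agree

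*Protocol*

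**What the plan says.** The design statement in Protocol 2.2 is clear: "This is a Phase 2b, double-blind, randomized, three-arm, placebo-controlled study". The SAP's study design text repeats the double-blind label.

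Protocol 8.3 then gives two adjacent sentences. The first is "Assignment to treatment group will be disclosed only after subject eligibility is confirmed and immediately prior to injection treatment". The second is "The Investigator, clinical staff and the subjects will be blinded to treatment group".

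The primary endpoint (2.3.1) is a C-CAT improvement of at least one grade at Day 84. On who rates it, section 4.11 says: "SMF ratings using the C-CAT will be conducted by the Investigator at screening and baseline", and the same role rates again on Days 28, 56 and 84. On the basis of the grade: "The C-CAT score will be based on the Investigator's clinical evaluation of the subject in the Frankfurt horizontal plane". No independent rater is named.

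On the injection day the Investigator selects the points and counts them: "The number of injections for each subject will be determined by the Investigator according to fullness of SMF" and "The Investigator will record the number of injections administered for each subject" (both 8.5). Step 6 of 8.5 has syringes filled with high dose, low dose or placebo, in the passive voice, without saying who fills them.

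On supply, 8.5 gives two vials per RZL-012 kit, 10.2 describes placebo as a one-vial kit with 4.8 mL per vial, and 10.4 speaks of kits of two vials and of two vials used for each subject.

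**The concern.** The first sentence of 8.3 speaks of the treatment group, not of a coded kit. The second excludes every site role that could receive that information. A coordinator or investigator trying to comply has to guess which sentence governs, at each of up to twelve sites.

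The person most exposed is the C-CAT rater. The grade is a whole number from 0 to 4, reached by looking at and palpating the chin, and one grade decides responder status. Knowledge of the arm could move that grade. The same role also assesses the relationship of adverse events to study drug (11.1), and the suspension rules in 11.2.4 count only drug-related events. A broken blind at this point could therefore affect both the primary comparison and the safety trigger, and neither could be repaired in the analysis.

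**Working it through.** **1. The plan's own figure, as background.** Inputs from Protocol 12.1: 70% and 35% response, two-sided alpha 0.05, 90% power. With a pooled variance under the null,

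n = [1.960 × √(2 × 0.525 × 0.475) + 1.282 × √(0.70 × 0.30 + 0.35 × 0.65)]² / 0.35² = (1.384 + 0.848)² / 0.1225 = 40.7, rounded up to 41.

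This reproduces the stated 41 per group. Going from 41 to 45 allows 1 − 41/45 = 8.9% dropout, as stated. The blinding point changes neither number.

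**2. The two sentences of 8.3 set side by side.**
- What is disclosed: assignment to treatment group. A kit or randomization number is not mentioned.
- When: after eligibility is confirmed and just before injection.
- To whom: not stated.
- Who stays blinded: Investigator, clinical staff, subjects.

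For both sentences to hold, the recipient must be someone outside those three categories. I looked in both documents for an unblinded pharmacist, preparer or injector, a code holder, a kit-number release, an independent C-CAT rater and a code-break procedure. None is described. The SAP adds nothing operational.

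**3. The kits.** One vial holds 4.8 mL and each point takes 0.15 mL, so one vial covers 4.8 / 0.15 = 32 points. The maximum in 8.5 is 36 points, or 36 × 0.15 = 5.4 mL. A single placebo vial would fall up to 0.6 mL short, so the one-vial description in 10.2 does not fit the volume range or the two vials per subject in 10.4. Either it is a slip, or placebo subjects need a second kit where active subjects need one. In the second case, anyone at the site who sees the kits could tell active from placebo, even with coded labels.

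**4. Size, as a hypothetical.** The documents give no rater-bias figure, so the shifts below are assumptions. Suppose the true response is 35% in both arms (the planned placebo rate), and that knowing the arm adds s points to the recorded high-dose rate. Take 45 per arm; the SAP counts a missing primary endpoint as failure, so dropouts stay in the denominator.

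For responder counts a (high dose) and b (placebo), with p = (a + b)/90,

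z = [(a − b)/45] / √[p(1 − p) × 2/45].

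The probability of each pair is Bin(a; 45, 0.35 + s) × Bin(b; 45, 0.35). Summing over all pairs with z > 1.96 gives significance in favour of high dose. Summing over |z| > 1.96 gives significance in either direction.

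| Assumed shift s | Significant, favouring high dose | Significant, either direction |
|---|---|---|
| 0 points | 2.6% | 5.3% |
| 5 points | 7.1% | 7.9% |
| 10 points | 15.7% | 15.8% |
| 15 points | 29.1% | 29.1% |

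With 41 per arm the favouring column is 2.5%, 7.1%, 16.0% and 29.9%, so the picture does not depend on dropout.

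**The case against.** The best defence is that the first sentence of 8.3 is a timing rule for allocation concealment: nothing about the assignment is to be known until eligibility is settled. It is phrased as a restriction, names no recipient, and is followed at once by an explicit list of who stays blinded. The double-blind label recurs in the title, the synopsis, section 2.2 and the SAP, and the internal safety committee reviews data blinded. On that reading this is loose wording.

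Much of this stands, and it rules out several stronger readings that a reader might infer:
- **That the protocol orders the Investigator to be unblinded, or that the trial is open-label for its primary rater.** No sentence says so. It follows only if the group itself is disclosed, and disclosed to the rater.
- **That the Investigator personally injects.** Section 8.5 is passive on who injects. The Investigator selects the points and records the count; only the rating role is explicit.
- **That the number of injections could be steered by arm.** In 8.5 the points are set at step 5 and syringes are filled at step 6, so disclosure just before injection can fall after the count is fixed. The count is also bounded at 28 to 36.
- **That the phase 2a study, whose physicians were not blinded, shows what would happen here.** That is another trial with another stated design.

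What the defence does not supply is a mechanism. Even on the benign reading, the documents do not say what reaches the site, who holds the code or who prepares the syringes, and the differing vial counts remain.

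**Conclusion.** Section 8.3 contradicts itself on a matter that bears directly on the primary endpoint, and nothing elsewhere in either document resolves it. That conclusion rests on the text alone and is firm.

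The consequence is conditional. Unblinding of the C-CAT rater requires that a site apply the first sentence literally, or that the kits differ visibly by arm and blinded staff handle them. The documents give no probability for either and no size for the resulting bias. The rise from 2.6% to between 7.1% and 29.1% therefore shows how sensitive the primary test would be to a modest rater shift. It does not estimate the effect of this wording, and the same arithmetic would apply to rater bias from any source.

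The point should be settled before sites act on the text, because the remedy is cheap and an unblinded primary rating cannot be undone.

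**What to change.** 1. In 8.3, replace the disclosure sentence with: *After eligibility is confirmed and the number and position of injection points are recorded, only a blinded kit number is released; the treatment group is not disclosed to the Investigator, clinical staff or subject.*
2. Name, by role, who holds the randomization code.
3. In 8.5 step 6, refer to the assigned kit in place of the three named treatments. Section 10.4 does not list the three treatments in this way and needs no matching change.
4. Reconcile the kit descriptions in 8.5, 10.2 and 10.4, so that kits hold the same number of vials and look the same in all three arms.

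The cost is a short protocol amendment. If the one-vial placebo kit is real and not a slip, a packaging correction is needed as well. Sample size, visits and analysis do not change.

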## **8.4 Pre-dose Evaluation (Day 0)**

Pre-dose assessments on Day 0 include the following:

- Vital signs
- AE assessment

## 8.5 Drug Administration

RZL-012 or placebo will be supplied as a single treatment in multiple sites of injection (32±4 injections). The injection dosing regimen and technique is crucial for the therapy safety.

The following procedures prior to injection into the SMF will be applied:

1. The lower face and anterior neck will be cleaned with an appropriate topical antiseptic.
2. Ice/cold pack or topical local anesthesia (i.e., lidocaine cream) may be used prior to drug administration to enhance subject's comfort.
3. The treatment area will be bounded superiorly by a line 1 cm inferior to the mandibular margin, laterally by the sternocleidomastoid muscles, and inferiorly by the hyoid bone.
4. Injection grid pattern will be applied by pressing the grid firmly onto the clean, dry skin, with the printed grid pattern facing the skin. The grid paper backing will be thoroughly wetted with a cotton pad soaked with sterile water. After 15 seconds, the grid cover will be peeled off.
5. An area of 32±4 adjacent injection points will be determined following the Investigator's evaluation.
6. Syringes will be filled with 1 mL RZL-012 high dose or low dose or placebo and the number of syringes will be compatible with the total volume of injection. Up to six (6) syringes for a total volume of 5.4 mL will be used.
7. All injections will be administered perpendicularly in 90 degrees, using a 1 mL Luer-lock syringe and a 29G x 1/2" needle, respectively.
8. The hole of the needle should be pointing into the fat layer and the injection direction should be towards the earth. An attempt to pull the plunger should be made prior to injecting to ensure no blood is coming out. If so, the plunger should be pushed down to inject 0.15 ml the medicine. The formulation is viscous; therefore, resistance is expected during injection.
9. Immediately following completion of the injections, an ice/cold pack will be applied for immediate pain relief. It will be held by the subject for at least two (2) minutes.
10. The Investigator will record the number of injections administered for each subject.

The injection pattern used will be based on an existing grid in the shape of the submental area, where distance between injection rows will be 1 cm and distance between the injection columns will be 1 cm.

The number of injections for each subject will be determined by the Investigator according to fullness of SMF but will not be lower than 28 injections or higher than 36 injections.

Each RZL-012 kit contains 2 vials that will be assigned to each subject:

- RZL-012 low dose will be provided in vials of 163 mg/4.8 mL (34 mg/mL)
- RZL-012 high dose will be provided in vials of 240 mg/4.8 mL (50 mg/mL)

Treatment with placebo will be conducted in the same manner as above.

The calendar date and 24-hour clock time of all doses will be recorded on the CRF.

## **8.6 Post-dose Evaluations (Day 0)**

Post-dose assessments on Day 0 include the following:

- Vital signs
- Concomitant medication
- AEs

Following completion of injection treatment, an ice/cold pack will be placed on the injected area for pain relief. Subjects will remain seated in the injection position for an additional ten (10) minutes after injections. Subjects will remain in the clinic up to 30 minutes (15-30 minutes) post dosing for medical supervision and AE assessments. During the confinement period, there are no restrictions in terms of activity or diet.

## **8.7 Study Visits (Days 1, 7, 28, and 56)**

Subjects will return to the clinical site for study visits on Days 1, 7, 28, and 56. Study visit assessments include the following:

- Vital signs
- Concomitant medication
- AEs
- Weight measurement (Day 56)
- Clinical laboratory tests (Days 1, 7, 28)
- Serum pregnancy test (in case pregnancy is suspected)

- ECG (Day 7)
- Caliper measurement of submental thickness (Days 28 and 56)
- S-CAT (Days 28 and 56)
- C-CAT (Days 28 and 56)
- 2D Photography (Days 1, 7, 28, and 56)
- Subject Global Assessment of Change (Days 28 and 56)
- Subject's satisfaction questionnaire (Day 28 and 56)
- Physician GAIS (Days 28 and 56)
- Subject impact questionnaire (Day 28 and 56)

In the case of clinically significant laboratory values at any visit, the subject will return for an unscheduled visit and a repeat of hematology and serum chemistry.

## **8.8 Final Visit (Day 84)**

Final study visit assessments include the following:

- ECG
- Physical Exam
- Concomitant medication
- AEs
- Clinical laboratory tests (including serum pregnancy test, in case pregnancy is suspected)
- Weight measurement
- Caliper measurement of submental thickness
- S-CAT
- C-CAT
- MRI
- 2D Photography
- Physician GAIS and physician assessment
- Subject Global Assessment of Change and self-assessment
- Subject's satisfaction questionnaires
- Subject impact questionnaires

## **8.9 Additional follow up of subjects:**

Following the completion of Day 84 visit of the last subject, subjects from three (3) chosen clinical sites will be followed up further twice up to a 1 year after injection to assess long term safety and duration of efficacy. The additional follow up visits will be at 6 and 12 months after injection.

These visits will include the following procedures:

- 2D Photography
- Physical exam of the treated area
- S-CAT
- C-CAT
- AEs

## 9.0 PREMATURE DISCONTINUATION FROM STUDY

A premature discontinuation from study will occur when a subject who signed informed consent ceases participation in this study, regardless of circumstances, prior to completion of the protocol. Subjects can be prematurely discontinued from the study for one of the following reasons:

- Failure to meet inclusion/exclusion criteria before receiving first dose of study drug has been administered
- Death
- Significant safety event that in the opinion of the Investigator warrants discontinuation. Raziel will attempt to follow up all subjects for safety.
- Lost to follow-up after every attempt has been made to contact the subject, including sending a registered letter
- Subject withdraws consent

The Principal Investigator and the Institutional Review Board/Ethics Committee (IRB/EC) reserve the right to prematurely terminate the study in the interest of subject safety and welfare. The Sponsor reserves the right to prematurely terminate the study at any time for administrative reasons.

## 10.0 PRODUCT SPECIFICATIONS

### 10.1 Description

RZL-012, illustrated in [Figure 1](#), is a novel synthetic molecule (termed RZL-012) that can help reduce fat content following its injection into the subcutaneous fat. Chemically, RZL-012 is 5-(3,6-dibromo-9H-carbazol-9-yl)-N,N,N-trimethylpentan-1-aminium chloride. RZL-012 is generated by a single step reaction and the final product is >97% pure.

RZL-012 is provided as a sterile liquid solution suitable for injection. RZL-012 investigational drug is intended to be administered as a single dose via multiple injections into the subcutaneous fat.

Placebo will be supplied as a vehicle control of tween-80, propylene glycol, benzyl alcohol and water.

